10.6 Clinical assessments and parameters

Assessment of tonsillitis will be performed according to the Local Tonsillitis Manifestation Scale. In detail the following symptoms will be investigated:

Local Tonsillitis Manifestation Scale

- Sore throat at swallowing (0 – absent, 1 – mild, 2 – moderate, 3 – severe / pronounced);
- Sore throat at rest, i.e. during the intervals between swallowing acts (0 – absent, 1 – mild, 2 – moderate, 3 – severe / pronounced);
- Throat irritation at rest, i.e. during the intervals between swallowing acts (0 – absent, 1 – mild, 2 – moderate, 3 – severe / pronounced);
- Cough associated with throat discomfort (0 – absent, 1 – mild, 2 – moderate, 3 – severe / troublesome).
- Posterior pharyngeal wall hyperaemia (0 – absent, 1 – mild, 2 – moderate, 3 – severe / pronounced);
- Palatine tonsils hyperaemia (0 – absent, 1 – mild, 2 – moderate, 3 – severe / pronounced);
- Palatine tonsils oedema (0 – absent, 1 – mild, 2 – moderate, 3 – severe / pronounced).

Diagnoses will be further refined using the Mclsaac Scale

Symptom	Score
Body temperature exceeding 38°C	+1
Absence of cough	+1
Painful anterior cervical lymph nodes	+1
Tonsillar oedema and/or exudate on tonsils	+1
Age 3–14 years old	+1
15–44 years old	0
>45 years old	- 1

Assessment of type of tonsillitis:

Score 0 – probability of group A β -haemolytic streptococcus (GABHS) infection is 1-2%;

Score 1 – probability of GABHS infection is 5-10%;

Score 2 – probability of GABHS infection is 11-17%;

Score 3 – probability of GABHS infection is 28-35%;

Score 4 – probability of GABHS infection is 51-53%;

Self-assessment of the quality of life by the patient.

- Sore throat at swallowing (0 –10 points VAS);
- Sore throat at rest, i.e. during the intervals between swallowing acts (0 –10 points VAS);
- Throat irritation at rest, i.e. during the intervals between swallowing acts (0 –10 points VAS);
- Cough associated with throat discomfort (0 –10 points VAS).

10.7 Appropriateness of measurements

All methods used for efficacy and safety assessments are standard methods for which reliability, accuracy and relevance have been documented (e. g. vital signs, body temperature, urine dip sticks etc.).

10.8 Handling and documentation of clinical data

The Principal Investigator has to ensure that all data required according to this protocol will be entered promptly in the patient's file, raw data sheets or directly in the CRF.

Co-ordinating Investigator, a member of the trial team will check data in the CRFs for formal correctness, completeness and legibility of the entries.

Documentation on clinical raw data, i.e. documentation on VAS will be collected on personal visits. A member of the trial team will check these raw data for formal correctness, completeness and legibility of the entries.

Entries on CRFs must be made with a black ball-point pen and must be legible. Pencils and correction fluids are not to be used. If corrections are necessary, they will be entered by a member of the trial team in the following manner: the wrong CRF entry will be crossed out; however, it must remain legible, and the correct entry will be placed next to the wrong entry. Changes and corrections to a CRF will be initialled and dated. For changes and corrections of direct CRF entries a reason must be provided, except in case of self-explanatory correction.

10.9 Risks related to the participation in the clinical trial

Blood withdrawal might occur during the study at the discretion of the investigator. Blood withdrawal might be painful or the subjects might temporarily become dizzy. Subjects may also experience intermittent complaints like re-bleeding or puncture site bruises, blood clot (thrombus) in the punctured vessel (rarely), puncture site infections (rarely) or mechanical nerve damage (very rarely)

10.9.1 Procedure related risks

10.9.2 Risks related to the investigational medicinal product

Imupret® oral drops

The investigational products Imupret® oral drops contain the ingredients given in sections 0 and 8.3.2.

According to the Summaries of Product characteristics the following site effects and interactions may occur during intake:

Side effects

Rarely gastrointestinal disorders (e.g. abdominal pain, nausea, vomiting) may occur. Allergic reactions (e.g. rash, itching, dyspnea) may also occur.

When taken together with preparations containing matricaria flowers and also in patients with hypersensitivity to other plants of the Composite family (e.g. Yarrow herb (*Achillea Millefolium*)) allergic reactions may occur. In case of any undesirable side effects the use of the medicinal product should be discontinued and a doctor should be consulted.

Interactions with other medicines and other forms of interaction

No interactions with other medicines have been reported. When using preparations which contain oak bark, the resorption of alkaloids and other alkaline medicinal agents may be reduced or blocked if taken together.

Overdose

No cases of intoxication due to overdose has been reported.

Reference treatment

At the discretion of the investigator, Paracetamol as single doses up to 500 mg – not more than 3-4 times daily will be prescribed. Moreover, at the discretion of the investigator, topical treatment with e.g. benzydamine, lidocaine (in case of severe sore throat) may be prescribed. In

case an antibiotic treatment will be necessary, the investigator may prescribe e.g. amoxicillin clavulanate, cephytryaxons etc.

As it is not yet known, what kind of prescription will be exactly done by the investigator, possible side effects and interactions are hardly to be described in here in the protocol. In any case the investigator has to inform the patient and (or) his/her parent(s) about the risks related to the intake of Reference medication according to the respective Summaries of Product Characteristics.

11 SAFETY ASPECTS

11.1 Definitions

11.1.1 Adverse event [AE]

An Adverse Event [AE] is defined as any untoward medical occurrence in a clinical trial subject to whom an Investigational Medicinal Product [IMP] has been administered and which does not necessarily have a causal relationship with this treatment.

An AE can therefore be any unfavourable and unintended sign (including an abnormal laboratory finding, refer to section 11.5), symptom, or disease temporarily associated with the use of an IMP, whether or not considered related to the IMP.

Examples of an AE include:

- A new sign, symptom, illness, or syndrome;
- Worsening of a pre-existing condition including either an increase in severity and/ or frequency of existing symptoms to a clinically significant exacerbation or the appearance of a new symptom during the AE reporting period;
- An effect of the IMP, including comparator or of concomitant medication;
- Signs, symptoms, or the clinical sequelae of a suspected interaction;
- Signs, symptoms, or the clinical sequelae of a suspected overdose of either IMP or a concomitant medication;
- An effect of a procedure required by the protocol;
- An accident or injury.

Examples of an AE do not include:

- A pre-existing condition, i.e. illnesses, clinical signs or symptoms, and/ or pathological laboratory values, which were already present at the first examination, unless an atypical course of the disease with exacerbation or increase in incidence of symptoms is observed;
- Medical or surgical procedures (e.g. endoscopy, appendectomy);
In general, these comprise therapeutic measures for conditions that require surgery. The condition for which the surgery is required is an AE if it occurs or is detected during the clinical trial. Planned surgical measures and the condition(s) leading to these measures are not AEs if the condition was known before the period of observation. In the latter case the condition should be reported as medical history.
- Worsening or deteriorations of common symptoms of the disease under study and/ or other expected clinical outcomes of the disease under study will generally not be recorded as AE.

AEs fall into the categories 'non-serious' or 'serious' (refer to section 11.1.2).

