Safety evaluation	
 - Adverse events (AEs), serious adverse events (SAEs) - Incidence of adverse drug reactions (ADRs)

	
- Overall assessment of tolerability
												

Methodology
	
 1. Medical history, demographic and anthropometric data at screening. 2. Complaints, patient questioning by organs and systems – at each visit, including any unscheduled visit and telephone contact. 
All complaints are assessed using a 4-point rating scale, beginning from the visit at which the complaint was identified for the first time.
 
 3. Physical examination: skin and visible mucosa examination, palpation of abdomen and lymph nodes, oropharyngoscopy are performed at each visit including any unscheduled visit. 
Symptoms are assessed using a 4-point rating scale, beginning from the visit at which the symptom was identified for the first time.
 
 4. Evaluation of probability of acute bacterial tonsillitis in accordance to McIsaac scale (sum of scores) 
  
 McIsaac scale (sum of scores)	The probability of the identification of β-hemolytic streptococcus in a smear from pharynx	
   
 -1 or 0	1%	
 
 1	10%	
 
 2	~17%	
 
 3	~35%	
 
 4 or 5	~50%	
  
 
 5. Complaints included in the Local Tonsillitis Manifestations Scale are assessed at each visit including any unscheduled visits 6. Symptoms included in the Local Tonsillitis Manifestations Scale are assessed at each visit 7. Axillary temperature assessment at each visit including any unscheduled visits. 8. Clinical blood count, urinalysis and blood chemistry according to the investigator's decision. 9. Self-assessment of the patient's state of health by him/herself and (or) his/her parents using a visual analogue scale is performed on a daily basis. 	McIsaac scale (sum of scores)	The probability of the identification of β -hemolytic streptococcus in a smear from pharynx	-1 or 0	1%	1	10%	2	~17%	3	~35%	4 or 5	~50%

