8.3 Trial treatment

The IMPs in this trial are Imupret® oral drops. The preparation is registered and available on the Ukrainian market without prescription. Therefore, the formulation, manufacturing, packaging and labelling of the IMPs follow the principles of Good Manufacturing Practice and currently valid national Ukrainian requirements. The detailed description covering all aspects regarding quality and safety of Imupret® oral drops are part of the respective Summary of Product characteristics.

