8.3.3 Reference treatment

All patients of the trial will undergo the reference treatment described below. However, only one of the two study groups (study group 1) will receive and add-on treatment with either Imupret® oral solution (see 0 and 8.3.2).

Reference treatment comprises instructions for patient's behavior as well as possible medical treatment when needed:

- Sparing diet with fractional feeding (5-6 times a day) in only small portions explicitly excluding coarse, spicy, or heavily digestible food
- At the discretion of the investigator, elimination of all factors irritating pharyngeal mucosa (e.g. thermal, chemical influence etc.)

At the discretion of the investigator, Paracetamol as single doses up to 500 mg – not more than 3-4 times daily

- At the discretion of the investigator, topical treatment like benzydamine, lidocaine (in case of severe sore throat)
- At the discretion of the investigator, antibiotic treatment in case it is indicated with e.g. amoxicillin clavulanate, cephalosporins (in case of prescription of antibiotics patients will be evaluated separately)

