11.1.3 Adverse reactions [AR]

An adverse reaction [AR] is any noxious and unintended response to an IMP irrespective of the dose administered. The phrase 'response to an IMP' means that a causal relationship between

the administration of the IMP and the occurrence of an AE is at least a reasonable possibility (refer to section 11.3).

All AEs will be judged by either the investigator or the sponsor as 'related' or 'not related' to the IMP.

An unexpected AR is an AR for which the nature or severity is not consistent with the applicable reference safety information for the Imupret® or Reference treatment provided in the Summaries of Product Characteristics.

When an unexpected AR also meets the definition of a SAE (refer to section 11.1.2), it is considered an unexpected serious AR. The co-ordinating investigator will report all suspected unexpected serious adverse reactions [SUSAR] to competent authorities, ethic committees, investigational sites, Bionorica SE as the supporter of this trial and other relevant recipients in all participating countries, in accordance with applicable reporting requirements.

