11.2 Period of observation

For the purpose of this trial, the period of observation for collection of AEs extends from signing of the informed consent form until the end of the trial (including follow-up period).

The investigator is not expected to actively monitor subjects for AEs once the clinical trial has ended. However, if the investigator becomes aware of a SAE in a subject after the end of the period of observation (regardless of the time elapsed from the trial end), and considers the event possibly related to prior trial treatment or procedures, the investigator should contact the Drug Safety department of Bionorica SE to determine how the AE should be documented and reported.

Regardless of the individual duration of the trial, any AE (including abnormal laboratory findings), irrespective of severity and whether serious or not, must be monitored by the investigator until it has satisfactorily subsided or has stabilized to such an extent that further marked improvement can no longer be expected or until a satisfactory medical explanation is found. The investigator must make every effort to contact subjects lost to follow-up. Attempts to contact such subjects must be documented in the subject's records (e.g., times and dates of attempted telephone contact, receipt for sending a registered letter).

This also applies to AEs still ongoing at the last visit of the individual patient. If necessary a further visit must be scheduled by the investigator.

It is the responsibility of the investigator to ensure that any necessary additional therapeutic measures and follow – up procedures are performed.

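### The AE definition contradicts the rules for collecting AEs, and judging causality against Imupret alone leaves ADR incidence not comparable between arms

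*Protocol*

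**What the plan says.** Section 11.1.1 defines an AE as "any untoward medical occurrence in a clinical trial subject to whom an Investigational Medicinal Product [IMP] has been administered", and its next sentence again links the event to use of an IMP. Section 11.1.2 defines an SAE as a kind of AE. Section 8.3 identifies the product: "The IMPs in this trial are Imupret® oral drops". Section 8.3.3 adds that "only one of the two study groups (study group 1) will receive" it on top of the reference treatment.

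On collection, section 11.2 states that "the period of observation for collection of AEs extends from signing of the informed consent form until the end of the trial". Section 11.3 has children questioned at every visit and asked to report any event, whatever its supposed link to the IMP. Sections 10.2, 10.4 and 10.5 schedule AE checks at Visits 2, 4 and 5, and the Visit 5 call expressly covers both groups.

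On causality, section 11.1.3 defines an adverse reaction as a response to an IMP and continues: "All AEs will be judged by either the investigator or the sponsor as 'related' or 'not related' to the IMP". Section 11.3 gives the CRF only those two codes. Yet the same section 11.1.3 judges whether a reaction is unexpected against "applicable reference safety information for the Imupret® or Reference treatment". The synopsis lists ADR incidence among the safety evaluations. Protocol 12.2.4 and the SAP's safety section describe AEs descriptively, including by relationship to the IMP.

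**The concern.** The title promises a comparison of safety and tolerability, and section 6.3 asks whether delaying antibiotics is safe in this age group. Both arms follow the delayed-prescription approach, so that question needs control-arm events and reactions to antibiotics as much as reactions to Imupret.

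Two things stand in the way. First, the definition a site would look up is narrower than the collection rules. Staff know which child has had no drops (section 8.4: no blinding), so a site that follows the definition may record less in control. That would make the Imupret arm look worse for reasons unrelated to the drug.

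Second, the only causality question is whether Imupret caused the event. Both arms may receive paracetamol, benzydamine, lidocaine or antibiotics, and section 10.9.2 accepts that reference medicines carry risks. Need for antibiotics is a main criterion (section 12.2.2), so exposure to them may differ by arm, yet a reaction to one has no place in the ADR count.

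**Working it through.** The plan gives no figure on this point to reproduce. The check is mainly a comparison of its own statements.

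**AE definition against collection rules**

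- Who is covered: 11.1.1 requires IMP to have been given. By 8.3 and 8.3.3 that means group 1 only. Sections 11.2, 11.3 and 10.5 do not restrict by arm.
- From when: 11.1.1 starts at the first dose and 11.2 at consent. The IMP is handed over at the end of Visit 1 (section 10.1), so the pre-dose gap is short.
- Within 11.1.1 itself, the examples of an AE include effects of comparator or concomitant medication, effects of protocol procedures, and accidents. These are wider than the headline sentence.
- In 11.3 the action-taken codes provide for an event arising while no IMP is being taken.

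The headline sentence is the outlier. Most of the operative text leads a site to record control events. The documents give no AE rate by arm. With an assumed common true rate of 1% to 20% and 100 children per arm, even collection gives an expected 100 × 0.01 = 1 to 100 × 0.20 = 20 events in each arm. A site network applying only the headline sentence would give 1 to 20 against 0. That is an outer bound, not what the protocol as a whole directs.

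**Causality rule against the ADR outcome**

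1. An ADR needs a related code (11.1.3).
2. Related means attributable to the investigational product (11.3).
3. That product is Imupret (8.3), and control children do not take it (8.3.3).
4. Every control event is therefore coded not related, and control ADRs are 0 of 100 whatever happens.
5. In group 1, a reaction to a reference medicine or antibiotic must be coded either as related to Imupret or as not related. Neither code records it as a reaction to the medicine that caused it.
6. The reference-treatment clause on expectedness in 11.1.3 then has nothing to act on, because such a reaction is not an adverse reaction under the definition given in the same section.

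**Illustration of scale (assumed rates; the documents give none).** Uncoded antibiotic reactions per 100 control children = 100 × share given an antibiotic × share of those who react.

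- Low: 100 × 0.20 × 0.05 = 1
- High: 100 × 0.40 × 0.15 = 6

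The structural zero in step 4 does not depend on these rates.

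**The case against.** The best reply is that section 11 should be read as a whole. Its examples count comparator effects as AEs, section 10.9.2 places the reference treatment under the heading of IMP risks, and section 11.1.3 refers to reference-treatment safety information. The authors seem to use IMP loosely, and a site following 11.2 and 11.3 would record control events. This stands for AEs and SAEs. A reader might infer from 11.1.1 that the control arm has no AEs or SAEs by definition, or that 100 of the 200 children fall outside safety capture. The collection rules do not support either inference.

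The loose reading does not rescue the ADR outcome. If IMP included the reference medicines, control would no longer be fixed at zero, but a single related code could not separate Imupret from paracetamol or an antibiotic. The listed outcome would remain uninterpretable as a between-arm comparison.

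It is also fair to say that zero Imupret-related reactions in children who never take Imupret is simply a fact, and that events coded not related remain on record with diagnosis, dates, intensity, seriousness and any corrective treatment. Antibiotic intake is documented too (section 10.2). Those events are missing from the ADR count, not from the data. Finally, no between-arm safety test is planned, so the risk is a misleading table and not a false significant result.

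**Conclusion.** The point holds in two limited parts. The AE definition, and the SAE definition built on it, contradict the collection rules, so control-arm and pre-dose events are exposed to inconsistent recording. How large that effect would be cannot be computed, because it depends on how sites resolve the conflict. ADR incidence is 0 in control by construction, taking the IMP to be what section 8.3 says it is, and reactions to reference medicines or antibiotics cannot be coded as drug reactions in either arm. The 1 to 6 uncoded reactions per 100 control children rest wholly on assumed rates.

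A reader might go further and conclude that the whole safety comparison favours control by construction. That is true only of ADRs and IMP-related events, not of all-cause AEs or SAEs. Nor should the illustrative antibiotic reactions be set against the 0.17% in section 6.2.1.2: that figure covers gastrointestinal complaints that ended Imupret intake in surveys, which is a different kind of event.

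This should be corrected, but it falls short of a must-fix: efficacy is untouched and control events are not removed from capture.

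**What to change.** - **11.1.1:** define an AE as any untoward medical occurrence in any consented child in either arm, whether or not IMP was given, to agree with 11.2. The SAE definition then follows.
- **11.1.3, 11.3 and the CRF:** record causality separately for Imupret and for reference or antibiotic medication, so that the expectedness clause has something to apply to.
- **12.2.4 and the SAP:** make all-cause AEs and SAEs by randomised arm the between-arm safety description. Report Imupret-related ADRs for group 1 only, and reference-drug or antibiotic ADRs for both arms. State the denominator for these tables: no safety set is defined, and the FAS also requires a dose of IMP.

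The cost is protocol and SAP wording, one extra causality field on the AE page and slightly more recording at sites. The field should be in place before data collection, since causality that was not captured at the time is hard to reconstruct.

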6.3 Description and rationale for conducting the trial

At present, there is minor evidence of using the phytoengineering-based drug product Imupret® in acute tonsillitis, pharyngitis and tonsillopharyngitis. The spectrum of its pharmacological properties includes antiviral, anti-inflammatory, and immunomodulatory action. The aggregate of these properties allows affecting almost all pathogenetic process links underlying the nosology in question, and favourable safety profile allows viewing Imupret as a basic therapeutic agent in treatment of non-bacterial forms of acute tonsillitis, pharyngitis, and tonsillopharyngitis. Our previous work showed that the use of Imupret in patients with non-bacterial tonsillitis accelerates regression of symptoms of tonsillitis and reduces the need for antibiotics. At the same time, there is a lack of studies, valid from the viewpoint of compliance with GCP standards have been conducted. Confirmation of high efficacy of Imupret in treatment of the above nosology group would be served as a justification for optimization of this nosology treatment scheme of delayed antibiotic prescription and recommendations for inclusion of this drug product into the national guidelines.

In the context of this clinical trial the two questions that are to be answered are:

1. Does Imupret®, taken during the diseases acute period help reduce the frequency of antibiotic use in children aged 6-12 ?
2. Does Imupret®, taken during the diseases acute period helps to accelerate the regression of symptoms in children aged 6-12?
3. Is the use of antibiotic delay technology safe for children aged 6-12 years?

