9.3 Exclusion criteria

- Score -1 to 3 according to Mclsaac Scale.
- Indication for hospitalization, including:
 - o purulent complications (peritonsillar abscess and others);
 - o severe general condition.
- Indication for immediate initiation of systemic antibiotic therapy
- patients at risk of developing severe complications, including e.g. clinically relevant concomitant diseases of heart, lungs, kidneys, liver, neuromuscular apparatus, cancer diseases, immunosuppression, diabetes mellitus, cystic fibrosis.
- suspected infectious mononucleosis (by clinical signs);
- use of systemic antibacterial or antifungal agents, systemic glucocorticosteroids, cytostatics, immunomodulatory drugs, "interferons" or interferon derivatives during the last 14 days prior to inclusion;
- presence of haemorrhagic or pronounced necrotic process in oral cavity or pharynx, including the lymphoid ring.
- Intolerability or individual hypersensitivity to any of the study drug ingredients and the reference treatment scheme.

Patients who refuse to sign the informed consent or who do not agree to passing on of their pseudonymous data to the monitor / CRO, the sponsor, and competent national or European community authorities must not be included in this trial.

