11.1.2 Serious adverse event [SAE]

A Serious Adverse Event [SAE] is an AE that at any dose (including overdose):

- results in death;
- is life-threatening¹;
- requires inpatient hospitalisation or prolongation of existing hospitalisation²;

- results in persistent or significant disability or incapacity³;
- is a congenital anomaly or birth defect;
- is a medical important event⁴.

- 1 'Life-threatening' means that the subject is at immediate risk of death at the time of the SAE; it does not refer to an AE which hypothetically might have caused death if it were more severe.
- 2 Hospital inpatient admission (for more than one calendar day) or prolongation of a hospital stay by at least one calendar day are required for the treatment of the AE, or occurs as a consequence of the AE.

Hospitalisation does not include the following:

- Emergency room/ accident and emergency/ casualty department visits;
- Out-patient/ same-day/ ambulatory procedures;
- Observation/ short-stay units;
- Rehabilitation facilities/ health resorts;
- Hospice facilities;
- Respite care (e.g. caregiver relief);
- Skilled nursing facilities;
- Nursing homes;
- Custodial care facilities;
- Clinical research/ phase I units;
- Hospitalisation in the absence of a precipitating, clinical AE:
 - Admission for treatment of a pre-existing condition not associated with the development of a new AE or with worsening of a pre-existing condition (e.g. for work up of persistent pre-existing lab abnormality);
 - Social admission (e.g. patient has no place to sleep);
 - Administrative admission (e.g. for annual physical examination);
 - Optional admission not associated with a precipitating clinical adverse event (e.g. for elective cosmetic surgery).

- 3 'Persistent or significant disability or incapacity' means a permanent or significant and substantial disruption of a person's ability to carry out normal life functions. This definition is not intended to include experiences of relatively minor medical significance such as uncomplicated headache, nausea, vomiting, diarrhoea, influenza, and accidental trauma (e.g. sprained ankle) which may interfere or prevent everyday life functions, but do not constitute a substantial disruption.

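### Protocol section 11.1.1 gives conflicting rules on recording disease-related events, so complications and serious worsening of tonsillitis may be under-recorded.

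*Protocol*

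**What the plan says.** Section 6.3 of the protocol lists as its third question: "Is the use of antibiotic delay technology safe for children aged 6-12 years". The safety outcomes in the synopsis are AEs, SAEs, adverse drug reactions and overall tolerability. Section 12.2.4 and the matching SAP text analyse AEs (frequency, intensity, relationship, outcome, seriousness) and laboratory values. Neither document has an outcome for complications or hospital admission.

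Section 11.1.1 treats disease-related events in two lists.

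- **Counted as AEs:** a new illness, and "Worsening of a pre-existing condition including either an increase in severity and/ or frequency of existing symptoms" where this amounts to a clinically significant exacerbation.
- **Not counted:** worsening of common symptoms of the disease under study, and "other expected clinical outcomes of the disease under study will generally not be recorded as AE".

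The second list contains two qualifications of its own. A pre-existing condition becomes reportable if its course is atypical, and a condition that needs surgery is an AE if it arises or is found during the trial.

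Seriousness is a property of AEs. Section 11.1.1 says "AEs fall into the categories 'non-serious' or 'serious", and section 11.1.2 opens with "A Serious Adverse Event [SAE] is an AE that at any dose (including overdose" before listing the criteria. Section 11.1.4 names no alert terms. Section 9.3 names "purulent complications (peritonsillar abscess and others" as a bar to entry; they do not appear again as an outcome.

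**The concern.** Children enter with a McIsaac score of 4 or 5, and antibiotics are held back at first. The main harm that such a delay could cause is progression or complication of the tonsillitis itself. The exclusion in section 11.1.1 concerns this class of event, and it leaves each site to decide which outcomes are expected. If a site applies it broadly, a complication can stay out of the AE record, and the plan gives no separate written route into the SAE record or the safety tables.

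Both arms use delayed prescription, so the main evidence on question 3 is the absolute number of such harms. Under-recording does not cancel in an absolute count as it might in a between-arm contrast. Because treatment is open, the judgement of what is expected could also differ by arm. A low count might then reflect the recording rule in part, and a statement that the delay was safe would rest on it.

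**Working it through.** The plan states no figure on this point, so the check is mainly a comparison of texts.

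**1. Does section 11.1.1 settle how a complication is classified?** Take a purulent complication that arises after entry. It can be read as a new illness, as a clinically significant exacerbation or, if it needs surgery, as a condition requiring surgery. Each reading makes it an AE. It can also be read as an expected outcome of tonsillitis, which is generally not recorded. No sentence says which list prevails, and expected is not defined. The text allows both answers.

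**2. Do the SAE rules override the exclusion?** Not explicitly. An SAE is an AE that meets a seriousness criterion (11.1.2), and the exclusion carries no exception for events that meet one. The admission criterion is itself tied to treatment of an AE or its consequence.

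**3. Is there another route?** Section 11.1.4 provides none. Section 11.3 elicits AEs by non-directive questioning, so nothing prompts for complications. Unscheduled visits for worsening (8.5) and withdrawal reasons (9.4.1) leave traces, but no analysis counts them as harms.

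**4. What is captured elsewhere?** Symptom scores, temperature and antibiotic need are efficacy variables (12.2.2, 12.2.3). The gap is therefore complications and serious disease outcomes, not ordinary symptom change.

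**5. Are reference children covered?** The AE definition speaks of an event "in a clinical trial subject to whom an Investigational Medicinal Product [IMP] has been administered", and section 8.3 says "The IMPs in this trial are Imupret® oral drops", which the reference arm does not receive. Against this, section 11.2 collects AEs from consent to the end of follow-up, section 11.3 asks at each visit, sections 10.2, 10.4 and 10.5 schedule AE checks (10.5 expressly for both groups), and section 11.3 allows for an AE in an IMP-free period. Collection in both arms is clearly intended; the definition is loosely worded.

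**6. Scale, for illustration only.** The documents give no complication risk. Let r be an assumed true risk and c an assumed share recorded, with n = 200 (both arms, since both delay). The chance of at least one recorded event is 1 − (1 − r·c)^200.

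| r (assumed) | all recorded, c = 1 | half recorded, c = 0.5 | none recorded, c = 0 |
|---|---|---|---|
| 0.5% | 1 − 0.995^200 = 63% | 1 − 0.9975^200 = 39% | 0% |
| 1% | 1 − 0.99^200 = 87% | 1 − 0.995^200 = 63% | 0% |
| 2% | 1 − 0.98^200 = 98% | 1 − 0.99^200 = 87% | 0% |

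Zero events in 200 would give a one-sided 95% upper bound of 1 − 0.05^(1/200) = 1.49%, but only if every event is recorded. If half were recorded, the same zero would bound the true risk at about 1.49% / 0.5 = 3.0%. Nothing in the documents fixes c; the last two columns are scenarios, not estimates.

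**The case against.** The best defence is that section 11.1.1, read as a whole, already captures the events that matter. The exclusion says generally and concerns common symptoms and expected outcomes. Children with purulent complications are barred at entry, which suggests that such complications are not the expected course in those enrolled. An abscess needing surgery is an AE by the section's own words, and admission would then make it an SAE. This defence stands to the extent that a careful site could properly record every such event, so loss is possible but not certain. It does not remove the conflict between the two lists or supply the missing rule for serious outcomes.

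A reader might infer that an excluded outcome can never become an SAE. That does not follow, because the same event may qualify as an AE under the other list.

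A reader might also infer that the reference arm's AE tables would be empty by definition. The consent-to-end collection period and the AE checks in both groups contradict that. What remains is a wording correction.

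Finally, question 3 is not repeated among the objectives in section 7, and neither arm receives immediate antibiotics. Better recording would therefore describe harms under delay but could not compare delay with immediate treatment. That is correct, and it limits what the fix can achieve.

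**Conclusion.** The concern holds as an internal contradiction that permits under-recording, possibly unevenly by site or arm, of complications and serious worsening of tonsillitis. It should be fixed; confidence is medium, because the outcome depends on how sites read the word expected.

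The size of the shortfall cannot be derived from the documents. The 63%, 87% and 98% figures assume risks of 0.5%, 1% and 2% and give only the chance that at least one event occurs among 200 children. It would be a mistake to read them as the share of events lost. The sample size is not affected.

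**What to change.** In section 11.1.1:

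- Limit the exclusion to ordinary symptom changes already scored on the Local Tonsillitis Manifestation Scale.
- State that complications of tonsillitis, such as purulent complications, and any disease-related event that meets a seriousness criterion are always recorded as an AE or SAE in both arms.
- Replace the restriction to recipients of an IMP with all randomised children, to match sections 10.2 to 10.5, 11.2 and 11.3.

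In section 12.2.4 and the SAP, add one table by arm through day 28 with complications, hospital admissions and unscheduled visits for worsening. Count the unscheduled visits as visits, not as AEs in themselves. Deleting the whole exclusion is not advisable: it would count efficacy outcomes a second time as AEs.

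The cost is a few sentences, one CRF line, one table and slightly more AE reporting. The report should present the result as a description of harms under delayed prescription, without claiming a comparison with immediate treatment.
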